11.0 Provisions to Monitor the Data to Ensure the Safety of Subjects

Safety will be monitored throughout the study based on the monitoring of adverse events, performing nasal exams, measuring vital signs (i.e. blood pressure, pulse) and weight, and through the collection of concomitant medication information.

The period of observation for collection of non-serious adverse events extends from the time the subject gives informed consent until the completion of the End-of-Study visit or Early Termination Visit. Serious adverse events (SAE) will be reported to the MUSC IRB and to the sponsor from the time of informed consent through 30 days after the last use of the SinuSonic. Adverse event data listings will be reviewed by Principal Investigator and the research team at regular intervals throughout the study.

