3.0 Intervention to be studied

- Initial intervention: Subjects will use the SinuSonic device for 3 minutes in the clinic setting.
- Secondary intervention: Subjects will use SinuSonic device twice daily for 3 minutes in the home setting for 14 days.
- Tertiary intervention: Subjects will continue to use the SinuSonic device twice daily for 3 minutes in the home setting for 2-4 weeks.

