6.0 Setting

Research will be conducted at the Medical University of South Carolina. Potential participants screening as well as the 2-week post treatment assessment will take place in the outpatient sinus clinics. The 4-6 week assessment will be done via emailing of surveys.

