9.0 Study Design / Methods

This study is designed as a pilot study.

Data will be collected by the ENT fellows as well as the subjects themselves throughout the entirety of the study. The data will consist of answers from subjects for questionnaires asked by the clinicians as well as self-reported answers from the subjects.

Safety will be monitored throughout the study based on monitoring of adverse events, performing nasal, measuring vital signs (i.e. blood pressure, pulse) and weight, and through collection of concomitant medication information.

The period of observation for collection of non-serious adverse events extends from the time the subject gives informed consent until completion of the End-of-study visit or Early Termination Visit. Serious adverse events (SAE) will be reported from the time of informed consent through 30 days after the last use of the SinuSonic. Adverse event data listings will be reviewed by SinuSonic at regular intervals throughout the study. In addition, SinuSonic will be alerted of Adverse Events of interest via automated emails programmed in the EDC system.

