9.1 Schedule of Events

Phase	Screening	Treatment		
		0	2	4-6
Week	0	0	2	4-6
Visit	1	2	3	4
Informed Consent	x			
Inclusion/Exclusion Criteria	x			
Medical History	x			
Height	x			
Rhinoscopy	x		x	
Vital Signs	x			
Pregnancy Test	x			
Distribution of SinuSonic	x			
NOSE Questionnaire	x		x	x
SNOT-22	x		x	x
TNSS Questionnaire	x		x	x
Global Assessment of Nasal/Sinus Problems	x	x	x	x
PNIF	x	x	x	

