19.0 DATA SAFETY MONITORING AND REPORTING

Safety data listings will be reviewed by Principal Investigator, Co-Investigators, and the research team at regular intervals throughout the study.

Safety will be monitored throughout the study based on monitoring of adverse events, performing nasal exams, measuring vital signs (ie blood pressure, pulse) and weight, and through collection of concomitant medication information.

The period of observation for collection of non-serious adverse events extends from the time the subject gives informed consent until completion of the End-of-study visit or Early Termination Visit. Serious adverse events (SAE) will be reported to the MUSC IRB and to the sponsor from the time of informed consent through 30 days after the last use of the SinuSonic. Adverse event data listings will be reviewed by the principal investigator, co-investigators, and the research team at regular intervals throughout the study.

All AEs, regardless of seriousness or relationship to SinuSonic use, spanning from the signature of the informed consent form until the end of the study as defined by the protocol for that patient, are to be reported to the Healthy Humming, LLC. All AEs which follow the MUSC IRB qualifications will also be reported to the MUSC IRB within 24 hours of site knowledge of the event.

The Investigator will take appropriate measures to follow all AEs until clinical recovery is complete and laboratory results have returned to normal, or until progression has been stabilized, or until death, in order to ensure the safety of the patients. This may imply that observations will continue beyond the last planned visit per protocol, and that additional investigations may be requested by the monitoring team up to as noticed by Healthy Humming, LLC.

In the case of occurrence of an SAE, the Investigator will immediately (within 24 hours) report the event to Healthy Humming, LLC and to the MUSC IRB, as applicable.

References

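### The SAE period runs to 30 days after last use, but no safety contact is scheduled after the emailed 4-6 week survey

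*Combined protocol and SAP*

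**What the plan says.** The SAE period appears in three places with the same length. Section 9.0 has "Serious adverse events (SAE) will be reported from the time of informed consent through 30 days after the last use of the SinuSonic". Section 11.0 gives the period as "from the time of informed consent through 30 days after the last use of the SinuSonic", and section 19.0 repeats it; both add the IRB and the sponsor as recipients. Collection of non-serious events stops sooner, at the End-of-Study or Early Termination Visit.

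Section 3.0 defines the use of the device. After one use in clinic, "Subjects will use SinuSonic device twice daily for 3 minutes in the home setting for 14 days", and then "Subjects will continue to use the SinuSonic device twice daily for 3 minutes in the home setting for 2-4 weeks".

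On contacts, section 6.0 says "Potential participants screening as well as the 2-week post treatment assessment will take place in the outpatient sinus clinics" and "The 4-6 week assessment will be done via emailing of surveys". The Schedule (9.1) places "Informed Consent" at Visit 1, week 0, and its last column is Visit 4, week 4-6. It has no later column and no adverse-event row.

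The form for that last assessment is Attachment 7, titled as a 5-week follow-up. It covers symptom lines, improvement ratings, comfort, willingness to reuse and recommend, TNSS and NOSE. Its explicit safety items are pain with use and a yes/no on bleeding.

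Section 19.0 also has the investigator follow adverse events until recovery or stabilisation, and adds "This may imply that observations will continue beyond the last planned visit per protocol". SAEs are to be reported within 24 hours.

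**The concern.** Planned use ends at about the time of the last scheduled contact. The 30 days that the protocol adds therefore fall almost entirely after anyone is due to ask the subject anything. Two further gaps make this harder to repair afterwards. No attached form records the date of last use, so the site may not know when the 30 days began. Section 18.0 covers storage and dispensing but describes no return of the device, so use could stop before the survey or go on after it. The last form also has no question that would bring out a hospital stay or another serious event unrelated to pain or bleeding.

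Safety is named in all three objectives in section 1.0. At stake is whether an SAE count for the stated period can be interpreted. With spontaneous reports alone, a subject who had no event cannot be told apart from one who was never asked, and a late event could go unreported to the IRB and the sponsor.

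**Working it through.** The plan gives no figure on this point, so there is none to reproduce. The check is day arithmetic.

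**Inputs**
- Start of the SAE period: consent at Visit 1, taken as day 0 (9.1).
- Planned home use: 14 days plus a further 14 to 28 days (3.0). This gives 14 + 14 = 28 to 14 + 28 = 42 days, which agrees with the 4-6 weeks in 6.0 and 9.1.
- Last scheduled contact: the emailed survey, day S = 28 to 42 (6.0, 9.1).
- Last scheduled clinic visit: week 2, day 14 (6.0).
- End of the SAE period: day of last use L + 30 (9.0, 11.0, 19.0).

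**Formula**
- Length of the SAE period = L + 30.
- Days after the last scheduled contact = max(0, L + 30 − S).
- Share = the second divided by the first.

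**Main case, last use on the survey day (L = S; an assumption)**
- Week 4: 30 / (28 + 30) = 30/58 = 51.7%.
- Week 5, the title of Attachment 7: 30 / (35 + 30) = 30/65 = 46.2%.
- Week 6: 30 / (42 + 30) = 30/72 = 41.7%.

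**How far the share moves if last use is on another day (survey still returned)**

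| Last use | Survey on day 28 | Survey on day 42 |
|---|---|---|
| 7 days after the survey | 37/65 = 56.9% | 37/79 = 46.8% |
| Survey day | 30/58 = 51.7% | 30/72 = 41.7% |
| 7 days before the survey | 23/51 = 45.1% | 23/65 = 35.4% |
| Day 14 | 16/44 = 36.4% | 2/44 = 4.5% |
| Day 0 | 2/30 = 6.7% | 0/30 = 0% |

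**Counted from the last clinic visit (last use on the survey day):** (58 − 14)/58 = 75.9% to (72 − 14)/72 = 80.6% of the period follows day 14. The only scheduled contact in that stretch is the emailed survey.

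**What the denominator does.** With zero SAEs among n subjects whose status is known, the one-sided 95% upper bound is 1 − 0.05^(1/n). For all 40 planned subjects (5.0) it is 7.2%. If 30 were confirmed (an assumption for illustration) it is 9.5%. If nobody is asked, n is unknown and no bound can be given.

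**The case against.** The strongest reply is that a reporting duty is not a promise to go looking. Section 11.0 describes collection of non-serious events over an observation period, whereas SAEs are to be reported, and section 19.0 ties IRB reporting to what the site knows. A reporting period longer than the visit schedule is common and is not in itself a contradiction. This stands: the protocol nowhere promises complete or prompted ascertainment over the 30 days. It does not answer the practical point, because the 24-hour rule can start only once someone learns of the event. The follow-up provision in 19.0 concerns events already known and schedules no contact to find new ones.

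A second reply is that not all the study's forms can be seen. Section 9.0 refers to an EDC system with automated alerts, and concomitant medication and early termination must be recorded somewhere. The consent pages, which may tell subjects to report later events, were removed before review. This also stands. The gap can be asserted only for the Schedule and the attached questionnaires.

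A third reply is that little depends on it. This is a pilot in 40 subjects, the primary objective concerns a single use in clinic, the device risks listed in 12.0 are local, and the uncovered days come after use has stopped. Section 10.0 plans safety summaries by time point, and its comparison points are 5 minutes, 2 weeks and 4-6 weeks, so no 30-day safety conclusion is planned. All of this limits the importance of the point, but does not remove the mismatch.

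A reader might infer that about half of the SAE period has no contact at all, or that about half of the SAEs would be missed. The documents support neither. Spontaneous reports are possible and known events may be followed. A share of calendar days is also not a share of risk. Nor do the documents support saying that a planned safety conclusion fails.

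**Conclusion.** The point holds as a gap between a stated reporting period and the means of filling it. Followed as written, the plan schedules no safety contact after the 4-6 week survey, and that survey asks neither for the date of last use nor about serious events. For subjects who use the device until the survey day, 42% to 52% of the SAE period is affected. In the other scenarios worked, the share runs from 0% (a subject who stops on day 0 and answers at week 6) to 56.9% (use continuing 7 days past a week-4 survey).

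The conclusion rests on three assumptions: consent on day 0, the survey returned within weeks 4-6, and no provision in unattached forms or the removed consent pages that fills the gap. The consequence is that any SAE count offered for the full stated period would lack a known denominator. The point is minor for a pilot of this size, but inexpensive to put right.

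**What to change.** - Add two fields to Attachment 7: the date of last use, and a yes/no serious-event question (hospital stay, emergency visit, other serious event).
- Add one emailed serious-event question 30 days after last use, by the route already used for the 4-6 week survey, and show it as a row in the Schedule (9.1). Where a subject is still using the device at the survey, the date of last use has to be asked again so that the message can be timed.
- Report the number who answered as the denominator for any SAE statement covering that period.
- If an EDC form or the consent form already does this, cite it in 11.0 and 19.0 instead of adding a second route.

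For subjects who answer, a contact at 30 days after last use brings the share of the period beyond the last scheduled safety contact to 0%. The cost is two form fields and one message per subject, with some non-response and a slightly later close-out. Only data collection changes; device use does not.

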12.0 Risks to Subjects

There is a risk of a loss of confidentiality of your personal information as a result of participation in this study.

There are risks to subjects using the SinuSonic device. Subjects may experience a degree of pain due to use of the device. This degree of pain is unknown. There may also be risk of nose bleeds or crusting around the nasal cavity.

The Rhinoscopy may activate the gag reflex. Additionally, nasal discomfort, nose bleeds, spasms, and coughing may also occur.

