4.0 Inclusion and Exclusion Criteria/ Study Population

The study population will consist of individuals present for care at the Otolaryngology clinics at the Medical University of South Carolina with nasal congestion, friends/family members of patients presenting for care at MUSC’s Otolaryngology clinics.

Inclusion Criteria

- Adults \geq 18 years of age
- Complaints of nasal congestion present for 2 weeks or more and a qualifying nasal congestion score of >5 (10 point VAS scale).

Exclusion Criteria

- Fixed structural cause of nasal congestion (moderate or severe septal deviation, moderate or severe nasal valve collapse, Grade 3-4 polyp)
- Inability to read and understand English
- Allergic sensitivity to silicone or any other component of device
- History of severe nose bleeding within last 3 months
- Anticoagulation (Aspirin ok)
- Known pregnancy
- Current nasal crusting or ulceration revealed on rhinoscopy
- Inability to perform treatment due to underlying medical condition

- Topical decongestant use in last week

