Attachment 5: 2-Week Follow Up

FOLLOW UP 2 WEEKS
PHYSICIAN ASSESSMENT

OVER THE LAST WEEK, HOW TROUBLESOME HAVE THE FOLLOWING SYMPTOMS BEEN? PLEASE PLACE A MARK ON THE LINE.	
	Not troublesome Worst thinkable/troublesome
Nasal blockage/obstruction/congestion	
Nasal discharge/drainage out of the front or back of nose	
Pain/pressure in nose or sinuses	
Sense of smell	
OVERALL ASSESSMENT OF NASAL AND SINUS PROBLEMS	

Change in nasal symptoms and use of device

Please rate changes in your nasal symptoms and use of device.

Symptom	None	Mild	Moderate	High
Improvement in nasal obstruction/stuffiness	0	1	2	3
Improvement in nasal drainage/discharge	0	1	2	3
Improvement in nasal or sinus pressure	0	1	2	3
Improvement in ability to smell	0	1	2	3
Use of the Device				
Pain with use of device	None	Mild	Moderate	Severe
Comfort and ease of use	Poor	Low	Moderate	High
Bleeding:	Yes	No		
Willingness to use again	Yes	No		
Willingness to recommend to friend/family	Yes	No		

Total Nasal Symptom Score

Please answer all questions to the best of your ability. This information will assist us in understanding and treating symptoms. Please rate how your symptoms have been over the **past week**.

Symptom	None	Mild: Symptom clearly present but easily tolerated	Moderate: Symptom bothersome but tolerable	Severe: Symptom difficult to tolerate – interferes with activities
Nasal congestion/obstruction	0	1	2	3
Runny nose/secretions	0	1	2	3
Nasal itching	0	1	2	3
Sneezing	0	1	2	3
Sleep difficulty with nasal symptoms	0	1	2	3

NOSE Scale

Please help us to better understand the impact of nasal obstruction on your quality of life by completing the following survey. Thank you!

Over the past **ONE month**, how much of a problem were the following conditions for you?

	Not a problem	Very mild problem	Moderate problem	Fairly bad problem	Severe problem
Nasal congestion or stuffiness	0	1	2	3	4
Nasal blockage or obstruction	0	1	2	3	4
Trouble breathing through my nose	0	1	2	3	4
Trouble sleeping	0	1	2	3	4
Unable to get enough air through my nose during exercise or exertion	0	1	2	3	4

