Attachment 7: 5-Week Follow Up**FOLLOW UP 5 WEEKS**

OVER THE LAST WEEK, HOW TROUBLESOME HAVE THE FOLLOWING SYMPTOMS BEEN? PLEASE PLACE A MARK ON THE LINE.		
	Not troublesome	Worst thinkable/troublesome
Nasal blockage/obstruction/congestion	◆————◆	◆————◆
Nasal discharge/drainage out of the front or back of nose	◆————◆	◆————◆
Pain/pressure in nose or sinuses	◆————◆	◆————◆
Sense of smell	◆————◆	◆————◆
OVERALL ASSESSMENT OF NASAL AND SINUS PROBLEMS	◆————◆	◆————◆

Change in nasal symptoms and use of device

Please rate changes in your nasal symptoms and use of device.

Symptom	None	Mild	Moderate	High
Improvement in nasal obstruction/stuffiness	0	1	2	3
Improvement in nasal drainage/discharge	0	1	2	3
Improvement in nasal or sinus pressure	0	1	2	3
Improvement in ability to smell	0	1	2	3
Use of the Device				
Pain with use of device	None	Mild	Moderate	Severe
Comfort and ease of use	Poor	Low	Moderate	High
Bleeding:	Yes	No		
Willingness to use again	Yes	No		
Willingness to recommend to friend/family	Yes	No		

Total Nasal Symptom Score

Please answer all questions to the best of your ability. This information will assist us in understanding and treating symptoms. Please rate how your symptoms have been over the **past week**.

Symptom	None	Mild: Symptom clearly present but easily tolerated	Moderate: Symptom bothersome but tolerable	Severe: Symptom difficult to tolerate – interferes with activities
Nasal congestion/obstruction	0	1	2	3
Runny nose/secretions	0	1	2	3
Nasal itching	0	1	2	3
Sneezing	0	1	2	3
Sleep difficulty with nasal symptoms	0	1	2	3

NOSE Scale

Please help us to better understand the impact of nasal obstruction on your quality of life by completing the following survey. Thank you!

Over the past **ONE month**, how much of a problem were the following conditions for you?

	Not a problem	Very mild problem		Moderate problem	Fairly bad problem	Severe problem
Nasal congestion or stuffiness	0	1		2	3	4
Nasal blockage or obstruction	0	1		2	3	4
Trouble breathing through my nose	0	1		2	3	4
Trouble sleeping	0	1		2	3	4
Unable to get enough air through my nose during exercise or exertion	0	1		2	3	4

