Attachment 8: SNOT-22 Survey**SNOT22 Survey**

	No problem	Problem as bad as it can be				
		Severe Problem	Moderate Problem	Mild or slight problem	Very mild problem	
3. Considering how severe the problem is when you experience it and how frequently it happens, please rate each item below on how "bad" it is by circling the number that corresponds with how you feel using this scale: →						
1. Need to blow nose	0	1	2	3	4	5
2. Sneezing	0	1	2	3	4	5
3. Runny nose	0	1	2	3	4	5
4. Cough	0	1	2	3	4	5
5. Post-nasal discharge	0	1	2	3	4	5
6. Thick nasal discharge	0	1	2	3	4	5
7. Ear fullness	0	1	2	3	4	5
8. Dizziness	0	1	2	3	4	5
9. Ear pain	0	1	2	3	4	5
10. Facial pain/pressure	0	1	2	3	4	5
11. Difficulty falling asleep	0	1	2	3	4	5
12. Wake up at night	0	1	2	3	4	5
13. Lack of a good night's sleep	0	1	2	3	4	5
14. Wake up tired	0	1	2	3	4	5
15. Fatigue	0	1	2	3	4	5
16. Reduced productivity	0	1	2	3	4	5
17. Reduced concentration	0	1	2	3	4	5
18. Frustrated/restless/irritable	0	1	2	3	4	5
19. Sad	0	1	2	3	4	5

20. Embarrassed	0	1	2	3	4	5
21. Loss of smell or taste	0	1	2	3	4	5
22. Nasal obstruction	0	1	2	3	4	5

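### Crusting is a named device risk, but the emailed 4-6 week form asks only about pain and bleeding, and no nasal exam is scheduled after week 2

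*Combined protocol and SAP*

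**What the plan says.** Section 12.0 gives three local risks of using the device: pain, and then "There may also be risk of nose bleeds or crusting around the nasal cavity". Section 4.0 treats crusting as something found on examination, since it excludes anyone with "Current nasal crusting or ulceration revealed on rhinoscopy".

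The row in the Section 9.1 schedule reads "Rhinoscopy x x". Its marks fall under screening and week 2, with none under weeks 4-6. Section 6.0 places screening and the 2-week assessment in clinic, and then states: "The 4-6 week assessment will be done via emailing of surveys".

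Attachment 7 is the only device-use form for the period after week 2. It carries a pain-with-use item and "Bleeding: Yes No". Attachment 5, the 2-week form, likewise has "Pain with use of device" and a bleeding item. Neither mentions crusting.

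Sections 9.0, 11.0 and 19.0 keep non-serious adverse event collection open from consent to the end-of-study or early termination visit. Section 9.0 adds that "SinuSonic will be alerted of Adverse Events of interest via automated emails programmed in the EDC system", without listing those events. Section 1.0 makes safety over 4 to 6 weeks a secondary objective, and Section 10.0 plans a safety summary at each time point.

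**The concern.** The plan puts a direct question to every subject for two of its three named local risks. The third relies on examination, and examination stops at week 2 while twice-daily use continues for another 2 to 4 weeks. For that stretch the forms shown contain no prompt for crusting.

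What is at stake is how the 4-6 week safety summary can be read. For pain and bleeding, each responder supplies an answer. For crusting, an absence of reports could mean that none occurred, that none was noticed, or that subjects did not think it worth volunteering. The documents do not describe how adverse events are elicited at the emailed assessment, so nothing in them separates these possibilities.

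**Working it through.** The plan states no figure on this point, so there is none to reproduce. The check sets the sections side by side and adds some simple arithmetic.

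**1. How each named risk is followed**

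| Risk (Section 12.0) | Up to week 2 | Weeks 4-6 |
|---|---|---|
| Pain | Item on Attachments 4 and 5 | Item on Attachment 7 |
| Nose bleeds | Item on Attachments 4 and 5; rhinoscopy at week 2 | Item on Attachment 7 |
| Crusting | Rhinoscopy at week 2 | No item; no exam scheduled |

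Subjects with crusting at entry are excluded, so crusting seen at week 2 would be new since screening. The gap therefore begins after week 2.

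**2. Does any other emailed item identify crusting?** Attachments 7 and 8 hold 5 VAS + 4 improvement + 5 device-use + 5 TNSS + 5 NOSE + 22 SNOT-22 = 46 items. None names crusting or sores. The nearest is "Thick nasal discharge" on the SNOT-22, which describes a different symptom.

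**3. How much planned use follows the last exam** (Section 3.0: twice daily for 14 days, then 2-4 more weeks)
- By week 2: 14 × 2 = 28 sessions.
- After week 2: 14 to 28 days × 2 = 28 to 56 sessions.
- Total: 56 to 84 sessions.
- Share after the last exam: 28/56 = 50% to 56/84 = 67%.

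**4. What a prompted item would allow.** With zero Yes answers from n responders, the exact one-sided 95% upper bound is 1 − 0.05^(1/n). Section 5.0 plans 40 subjects. No response rate is given, so the lower values of n are assumptions.
- n = 40: 1 − 0.05^(1/40) = 7.2%
- n = 30: 1 − 0.05^(1/30) = 9.5%
- n = 20: 1 − 0.05^(1/20) = 13.9%

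**5. Why prompting matters for a zero count (illustration only).** Assume that 5% of 40 users develop crusting and that a fraction s of cases gets recorded. The chance of at least one record is 1 − (1 − 0.05s)^40.
- s = 1: 0.87
- s = 0.5: 0.64
- s = 0.25: 0.40

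Both the 5% and the values of s are assumed. The illustration shows only that a zero is less informative when capture is incomplete.

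**The case against.** The strongest reply is that crusting after week 2 is already reportable. Collection of non-serious events stays open, and Section 19.0 requires every adverse event to be passed to the company whatever its seriousness or relation to the device. This stands. A reader might infer that such crusting could not be recorded at all, or that no rate could be formed. The documents support neither: reported cases can be counted, and treated subjects or survey responders supply a denominator. What is missing is a prompted answer.

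A reader might also infer that crusting is missed throughout follow-up, because no follow-up form shown asks about it. That goes too far. Rhinoscopy covers week 2, and new crusting is hardly a realistic question five minutes after one 3-minute use. Only Attachment 7 matters here.

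Other parts of the reply also stand. No adverse event form, rhinoscopy form or specification of the events of interest appears in the documents, and one of these may already prompt for crusting. The bleeding item states no recall period, so a Yes at 4-6 weeks cannot be dated to before or after week 2, and the contrast with crusting is less clean than it looks. Nor do the documents say that the emailed survey is the last contact: serious events are reported until 30 days after last use, and events are followed to recovery or stabilization.

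Sections 11.0 and 19.0 say that nasal exams are part of safety monitoring throughout the study. That does not close the gap, because the schedule places none after week 2 and an emailed survey cannot supply one.

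**Conclusion.** The point holds as a modest, cheaply corrected gap on one form. Followed as written, and on the forms shown, the plan asks no subject about crusting after week 2, although it names crusting as a device risk and makes 4-6 week safety an objective. A zero at that time point would be a statement about reports received.

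The 50-67% of sessions after the last exam indicates how much use is involved. It is not an estimate of harm, since the documents give neither a rate nor a severity for crusting. The 7.2-13.9% bounds describe what the added item could deliver at assumed responder counts; they do not measure a loss in the current plan, which intends only descriptive safety summaries in a 40-subject pilot.

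A reader should not carry the point over to the single-use primary objective or to any efficacy comparison. Neither depends on crusting after week 2. The conclusion rests on Attachment 7 being the form emailed at 4-6 weeks, and on no form outside the documents already asking the question.

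**What to change.** Add one line to Attachment 7, beside the bleeding item: *Nasal crusting or sores since your week 2 visit: Yes / No*. The recall period needs stating because the bleeding item has none and the VAS items on the same form cover only the preceding week. Attachment 5 needs no change, since rhinoscopy covers week 2.

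In the 4-6 week safety summary, report the result as self-reported crusting: the number answering Yes over the number who answered.

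The cost is one extra line on a survey already being sent, with no added visit or procedure. Self-report will miss crusting the subject does not notice, so a No from every responder would not establish its absence. If an adverse event form not shown already asks about crusting at this contact, the line would be a duplicate and can be left out.
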